1 PROTOCOL SUMMARY

Vortex Temporary Percutaneous Transvalvular Circulatory Support System Feasibility Study: Vortex Feasibility Study													
Study Objective(s)	To evaluate the feasibility and safety of the Vortex Temporary Percutaneous Transvalvular Circulatory Support System (Vortex System) in subjects undergoing elective high-risk percutaneous coronary intervention (HR-PCI)												
Planned Indication(s) for Use	The Vortex System is indicated to provide temporary (≤ 4 hours) circulatory support in subjects undergoing elective high-risk percutaneous coronary intervention (HR-PCI).												
Test Device	The Vortex System is a minimally invasive device that is in direct contact with the heart while in use. Components are summarized below.												
	
  
 Component	Description	
   
 [REDACTED]	[REDACTED]	
 
 [REDACTED]	[REDACTED]	
 
 [REDACTED]	[REDACTED]	
 
 [REDACTED]	[REDACTED]	
 
 [REDACTED]	[REDACTED]	
  
	Component	Description	[REDACTED]	[REDACTED]	[REDACTED]	[REDACTED]	[REDACTED]	[REDACTED]	[REDACTED]	[REDACTED]	[REDACTED]	[REDACTED]
	Component	Description											
	[REDACTED]	[REDACTED]											
	[REDACTED]	[REDACTED]											
	[REDACTED]	[REDACTED]											
[REDACTED]	[REDACTED]												
[REDACTED]	[REDACTED]												
[REDACTED]	[REDACTED]												
[REDACTED]	[REDACTED]												
[REDACTED]	[REDACTED]												
[REDACTED]	[REDACTED]												

Vortex Temporary Percutaneous Transvalvular Circulatory Support System Feasibility Study: Vortex Feasibility Study	
Study Design	
The Vortex Feasibility Study is a prospective, open-label, single-arm study designed to assess the safety and feasibility of the Vortex System to provide temporary (≤ 4 hours) circulatory support in subjects undergoing HR-PCI.
 
The study design is summarized in the figure below.
 
* Subjects who provide informed consent are considered enrolled as soon as an attempt is made to insert any part of the Vortex System into the subject's femoral artery. ‡ ≤ 72 hours or discharge, whichever comes first
 
Vortex Feasibility Study Design Overview
 
The Vortex study will be conducted in accordance with the International Standard ISO 14155:2020 Clinical Investigation of Medical Devices for Human Subjects – Good Clinical Practice; European Medical Device Regulations; ethical principles that have their origins in the Declaration of Helsinki; and pertinent individual country/state/local laws and regulations. The study shall not begin until the required approval/favorable opinion from the Independent Ethics Committee (IEC)/Human Research Ethics Committee (HREC) and/or regulatory authority has been obtained, if appropriate.

Planned Number of Subjects / Investigational Centers / Countries	There will be up to 10 subjects enrolled in up to 3 centers in Australia and Europe.
Primary Endpoint	
The primary endpoint consists of Technical Success and Clinical Success, defined as follows.
 
Technical Success
 
 • Successful delivery of the device to the correct anatomical position; and

Vortex Temporary Percutaneous Transvalvular Circulatory Support System Feasibility Study: Vortex Feasibility Study	
	
 • Successful operation and removal of the Vortex circulatory support system 
Clinical Success
 
 • No conversion to open heart surgery; and • No in-hospital mortality
Additional Measurements	
Safety events will be collected through 72 hours post-procedure or hospital discharge, whichever comes first, as listed below.
 
 • Stroke/transient ischemic attack (TIA; see Note 1 below) • Cardiac tamponade • Cardiac death (see Note 1 below) • Myocardial infarction (MI) • Bleeding complications: Type 3–5 based on the Mechanical Circulatory Support Academic Research Consortium (MCS-ARC) definitions^a (see Note 1 below) • Acute kidney injury (AKI; based on the AKIN System Stage 3 [including renal replacement therapy] or Stage 2) • Major vascular complications (see Note 1 below) • Any device-related adverse event (adverse device effect [ADE]/serious adverse device effect [SADE]) • Any procedure-related adverse event • Any adverse event related to management practices • Any adverse event related to patient specific adherence • Any unanticipated serious adverse device effect (USADE) 
Note 1: Death, stroke, bleeding complications, and major vascular complications are adjudicated by an Independent Medical Reviewer (IMR).
 
a: Kormos RL, et al. J Heart Lung Transplant 2020;39:735-50

Method of Assigning Patients to Treatment	
Subjects who provide written informed consent and are confirmed eligible for the study are considered enrolled in the study as soon as an attempt is made to insert any part of the Vortex System into the subject’s femoral artery (e.g., Vortex sheath).

Vortex Temporary Percutaneous Transvalvular Circulatory Support System Feasibility Study: Vortex Feasibility Study	
Follow-up Schedule	Follow up will occur through 72 hours after enrollment or hospital discharge, whichever comes first.
Study Duration	Enrollment/total study duration may be completed in approximately 12 months.
Participant Duration	The study duration for each subject is expected to be through 72 hours or hospital discharge, whichever comes first.
Index Procedure	The Vortex sheath will be inserted percutaneously into the femoral artery. The Vortex wire and Vortex pump will pass through this sheath during the procedure and will be advanced through the aorta, across the aortic valve, and into the left ventricle. The wire will be withdrawn before the pump is turned on, but the sheath and pump will stay in place throughout the HR-PCI procedure and will be withdrawn as soon as the mechanical circulatory support is deemed to be unnecessary.
Statistical Methods	
Primary Statistical Hypothesis	There is no formal statistical hypothesis in this observational feasibility study.
Statistical Test Method	
Descriptive statistics will be used for baseline, procedure, and follow-up data collected during the study.
 
The primary endpoint and additional measurements will be analyzed on an intention-to-treat (ITT) basis and a per-protocol basis. Analysis sets are listed below. Subjects are considered enrolled in the study as soon as an attempt is made to insert any part of the Vortex System into the subject's femoral artery.
 
 • ITT: This population includes all subjects who sign an Informed Consent Form (ICF) and are enrolled in the study, whether or not a study device is successfully inserted and used. • Per-protocol: This population includes all ITT subjects in whom the device is successfully advanced across the aortic valve into the left ventricular outflow tract and turned on.

Vortex Temporary Percutaneous Transvalvular Circulatory Support System Feasibility Study: Vortex Feasibility Study

Sample Size
Parameters

This is a prospective, multicenter, non-randomized feasibility study with no formal pre-specified hypothesis and therefore sample size estimates are not applicable. In order to support the stated objectives of this feasibility study, the study sample size has been limited to a maximum of up to 10 subjects enrolled.

2 INTRODUCTION

The Vortex System is intended to support stable subjects undergoing HR-PCI by temporarily decreasing the load on the heart and ensuring adequate organ perfusion. The statistical analysis for this first-human-use study will provide data to assess device safety and technical feasibility of device use in subjects undergoing elective HR-PCI.

3 ENDPOINT ANALYSIS

There is no formal statistical hypothesis for the endpoints. Descriptive statistics will be provided.

3.1 Primary Endpoint

The primary endpoint consists of Technical Success and Clinical Success.

Technical Success

- Successful delivery of the device to the correct anatomical position; and
- Successful operation and removal of the Vortex circulatory support system

Clinical Success

- No conversion to open heart surgery; and
- No in-hospital mortality

3.1.1 Hypotheses

There is no formal statistical hypothesis for the primary endpoint.

3.1.2 Sample Size

To support the stated objective of this feasibility study, while also limiting the potential exposure to risk of study subjects, the study sample size has been arbitrarily set at a maximum of 10 subjects enrolled.

3.1.3 Statistical Methods

Descriptive statistics for the primary endpoint will be provided including numerator, denominator, and proportion.

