4.2. Study Rationale

The Vortex System is intended to support stable subjects undergoing HR-PCI by temporarily decreasing the load on the heart and ensuring adequate organ perfusion. Prophylactic use of the Vortex System during HR-PCI procedures should improve patient hemodynamics and may improve patient outcomes. The Vortex design provides a therapeutic approach and mechanism of action like that of commercially available devices but may also provide improved conformation to subject anatomy and a less complex arrangement during the interventional procedure. The Vortex design has been assessed in animals, in benchtop models, and via computational simulations. However, there are currently no animal or bench models that can adequately represent the disease state of subjects undergoing HR-PCI. Therefore, a first-human-use study is required to assess and confirm device safety, and technical feasibility of device use during the HR-PCI procedure to aid in optimization of device functionality and design.

5. Device Description

The Vortex System is a minimally invasive, temporary device that is in direct contact with the heart while in use. It is intended to run for up to 4 hours to support subjects undergoing HR-PCI as determined by an appropriately trained medical team. The Vortex design provides a therapeutic approach and mechanism of action similar to that of the commercially available Impella[®] devices (Abiomed, Inc., Danvers, MA, USA). A summary of the device is provided below. Additional information on the device can be found in the Investigator's Brochure and Instructions For Use (IFU).

5.1. *Vortex System*

[Redacted]

Table 5.1-1: Summary of Vortex System Components

Component	Description ^a
[Redacted]	[Redacted]
[Redacted]	[Redacted]
[Redacted]	[Redacted]
[Redacted]	[Redacted]

a: Detailed information is provided in the Investigator’s Brochure.

5.1.1. **Vortex Pump**

[Redacted]

[Redacted]

[Redacted]

[Redacted]

[Redacted]

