3.2.1 Statistical Methods

Descriptive statistics will be provided including numerator, denominator, and proportion.

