4 GENERAL STATISTICAL METHODS

4.1 Analysis Sets

The primary endpoint and additional measurements will be analyzed on an intention-to-treat (ITT) basis and a per-protocol basis. Analysis sets are listed below. Subjects are considered enrolled in the study as soon as an attempt is made to insert any part of the Vortex System into the subject's femoral artery.

- ITT: This population includes all subjects who sign an ICF and are enrolled in the study, whether or not a study device is successfully inserted and used.
- Per-protocol: This population includes all ITT subjects in whom the device is successfully advanced across the aortic valve into the left ventricular outflow tract and turned on.

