5 ADDITIONAL DATA ANALYSES

Additional study data collected will be summarized using descriptive statistics (e.g., mean, standard deviation, n, minimum, maximum) for continuous variables and discrete variables (e.g., numerator, denominator, proportion). The main analysis dataset is ITT.

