5.7 Changes to Planned Analyses

Any changes to the planned statistical analyses made will be documented in a Statistical Analysis Plan approved prior to database lock.

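### With at most 10 subjects, should the SAP pre-specify confidence intervals for the primary endpoint and the safety events?

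*SAP*

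**What the plan says.** For the primary endpoint, SAP 3.1.3 reads: "Descriptive statistics for the primary endpoint will be provided including numerator, denominator, and proportion". For the safety events, SAP 3.2.1 reads: "Descriptive statistics will be provided including numerator, denominator, and proportion". SAP 5, on the remaining data, gives summaries for "discrete variables (e.g., numerator, denominator, proportion"). The first two lists open with *including* and the third with *e.g.*, so none is closed. Protocol 11.1.1.3 and 11.3 likewise call for descriptive statistics, with frequencies or proportions for discrete data. Neither document mentions a confidence interval.

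On size, SAP 3.1.2 says "the study sample size has been arbitrarily set at a maximum of 10 subjects enrolled". The per-protocol set may be smaller still, because it holds "all ITT subjects in whom the device is successfully advanced across the aortic valve into the left ventricular outflow tract and turned on" (SAP 4.1). SAP 7.4.3 puts every subject of the relevant set in the denominator.

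On aim, Protocol 4.2 says: "a first-human-use study is required to assess and confirm device safety, and technical feasibility of device use during the HR-PCI procedure to aid in optimization". SAP 2 says the analysis "will provide data to assess device safety and technical feasibility of device use". Protocol 11.1.1.1 and SAP 3.1.1 state that there is no formal hypothesis.

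**The concern.** A proportion from 10 or fewer people is very imprecise, and it is easiest to misread at its extremes, which are the results a device study hopes for. A table that shows a safety event at 0% or Technical Success at 100% can look conclusive when it excludes little. The reference in Protocol 4.2 to confirming device safety seems to invite that reading.

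There is also a question of method. If an interval were added after the data were seen, the choice of formula would matter at zero events, and the plan fixes none. At stake is the interpretation of the results. The counts themselves would be right either way.

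**Working it through.** **Inputs.** The maximum n is 10 (Protocol 11.1.1.2, SAP 3.1.2). The documents give no confidence level, so two-sided 95% is assumed (α = 0.05). The sizes n = 8 and n = 5 are assumed examples of a smaller analysis set. Protocol 4.1.2 quotes in-hospital mortality of 3.4% and 2.6% from two registries of a similar device. The plan has no precision figure of its own to reproduce, since it calls the sample size arbitrary.

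**Exact (Clopper-Pearson) limits.** With zero events the upper limit is 1 − (α/2)^(1/n). With all successes the lower limit is (α/2)^(1/n).

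| n | Zero events: upper limit | All successes: lower limit |
|---|---|---|
| 10 | 1 − 0.025^(1/10) = 30.8% | 0.025^(1/10) = 69.2% |
| 8 | 1 − 0.025^(1/8) = 36.9% | 0.025^(1/8) = 63.1% |
| 5 | 1 − 0.025^(1/5) = 52.2% | 0.025^(1/5) = 47.8% |

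From beta quantiles, 1/10 gives 0.3% to 44.5% and 9/10 gives 55.5% to 99.7%.

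**Dependence on method at 0/10.** The upper limit is 30.8% exact, 27.8% Wilson (z²/(n + z²) = 3.8415/13.8415) and 21.7% Jeffreys. The simple normal approximation gives 0 ± 1.96 × √(0 × 1/10), which collapses to 0%.

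**Chance of a clean result.** P(no event in 10) = (1 − p)^10. At the registry mortality rates this is 0.966^10 = 71% and 0.974^10 = 77%. At assumed event rates of 10% and 20% it is 0.9^10 = 35% and 0.8^10 = 11%.

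The imprecision is therefore real and large. The next question is whether the plan hides it or relies on ignoring it.

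1. *Is anything lost?* An exact interval is a function of numerator, denominator and level only. SAP 3.1.3 and 3.2.1 require the first two, and SAP 7.4.3 fixes the denominator. A reader sees 0/10 and can obtain 30.8%.
2. *Does a decision depend on it?* No performance goal, success threshold or go/no-go rule appears in either document. SAP 5.2 plans no interim analysis. The termination criteria in Protocol 21.1.1 are qualitative and use no estimated rate.
3. *Does the plan claim confirmation?* Protocol 6.1 and Table 6.4-1 speak of evaluating feasibility and safety, Protocol 7 and SAP 2 of assessing them, and Protocol 7.3 of an assessment. Only Protocol 4.2 adds the stronger verb, in a background sentence whose stated end is to optimise the device.
4. *Is an unsuitable method proposed?* No. The collapse to 0% belongs to a formula that neither document mentions.
5. *Would intervals everywhere help?* Two primary components and 12 listed measurements in two sets make (2 + 12) × 2 = 28 intervals from at most 10 people. The one for Technical Success in the per-protocol set would be hard to interpret. That set requires the device to have crossed the valve and been turned on, which overlaps the delivery and operation parts of the endpoint, so some failures are removed by selection.

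**The case for a change.** The best case for a change is that it costs almost nothing: one sentence in each of two SAP sections and one output column. An interval tests nothing, so the lack of a hypothesis is no reason to leave it out. Many clinical readers will not work one out from a count. The protocol's own registry rates make a death-free result likely (71% to 77%), so the reassuring table is the one to expect. Naming the exact method beforehand would also prevent a later choice that shifts the upper limit at 0/10.

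Much of this stands as advice on reporting. Intervals on the ITT results would help a reader who skips the denominator. It does not show that the plan is deficient. The analyses as written give correct results, the counts needed to judge precision are mandatory, and the open wording already permits an interval. If the sponsor wants one planned, SAP 5.7 gives the route: "Any changes to the planned statistical analyses made will be documented in a Statistical Analysis Plan approved prior to database lock". The wording in Protocol 4.2 is a fair editorial remark, but it governs no analysis, and an amendment for that word alone would need the ethics and agency review described in Protocol 15.3.

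**Conclusion.** No change is needed. With at most 10 subjects the estimates are very imprecise: at an assumed two-sided 95% level, the exact limits are 0% to 30.8% for 0/10 and 69.2% to 100% for 10/10, and wider if fewer subjects are analysed. The plan does not conceal this. It reports numerator and denominator for every proportion, draws no inference and attaches no decision to the results. Adding intervals would change no result and no conclusion the plan is set up to draw.

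An analyst who reports an interval anyway would sensibly use the exact method in the ITT set and leave out Technical Success in the per-protocol set. The verb in Protocol 4.2 is a minor variance from the stated objective. The judgement rests on the study remaining descriptive; it would differ if a performance goal or a success criterion were attached to these proportions.

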3.2 Additional Measurements

Safety events will be collected through 72 hours post-procedure or hospital discharge, whichever comes first, as listed below. Death, stroke, bleeding complications, and major vascular complications are adjudicated by an Independent Medical Reviewer (IMR).

- Stroke/transient ischemic attack (TIA)
- Cardiac tamponade
- Cardiac death

- Myocardial infarction (MI)
- Bleeding complications: Type 3–5 based on the Mechanical Circulatory Support Academic Research Consortium (MCS-ARC) definitions
- Acute kidney injury (AKI; based on the AKIN System Stage 3 [including renal replacement therapy] or Stage 2)
- Major vascular complications
- Any device-related adverse event (adverse device effect [ADE]/serious adverse device effect [SADE])
- Any procedure-related adverse event
- Any adverse event related to management practices
- Any adverse event related to patient specific adherence
- Any unanticipated serious adverse device effect (USADE)

3.2.1 Statistical Methods

Descriptive statistics will be provided including numerator, denominator, and proportion.

4 GENERAL STATISTICAL METHODS

4.1 Analysis Sets

The primary endpoint and additional measurements will be analyzed on an intention-to-treat (ITT) basis and a per-protocol basis. Analysis sets are listed below. Subjects are considered enrolled in the study as soon as an attempt is made to insert any part of the Vortex System into the subject's femoral artery.

- ITT: This population includes all subjects who sign an ICF and are enrolled in the study, whether or not a study device is successfully inserted and used.
- Per-protocol: This population includes all ITT subjects in whom the device is successfully advanced across the aortic valve into the left ventricular outflow tract and turned on.

4.2 Control of Systematic Error/Bias

The selection of subjects will be made from the Investigator's usual case load. Subjects who are candidates for HR-PCI, provide written informed consent, and are eligible to be treated with the Vortex System will be evaluated for enrollment in this study. The study center's heart team assessments and imaging measurements before device placement will contribute to the determination of subject eligibility for the study.

To control for inter-observer variability, an independent IMR will adjudicate mortality, stroke, major vascular complications, and bleeding endpoints.

4.3 Number of Subjects per Investigative Site

There will be up to 10 subjects enrolled in up to 3 centers in Australia and Europe. There is not limit on number of subjects per investigative site.

5 ADDITIONAL DATA ANALYSES

Additional study data collected will be summarized using descriptive statistics (e.g., mean, standard deviation, n, minimum, maximum) for continuous variables and discrete variables (e.g., numerator, denominator, proportion). The main analysis dataset is ITT.

5.1 Other Endpoints/Measurements

Additional analysis may include analyses for the following data:

- Subjects disposition
- Baseline
- Procedure and device performance
- Medication
- Adverse event
- Protocol deviation

5.2 Interim Analyses

No interim analysis is planned.

5.3 Subgroup Analyses

No subgroup analysis is planned.

5.4 Justification of Pooling

No poolability analysis is planned for the small study with 10 subjects.

5.5 Multivariable Analyses

No multivariate analysis is planned.

5.6 Other Analyses

Subject listings with selected variables may be provided (e.g., patient characteristics, procedure and device related data, and events or outcomes)

5.7 Changes to Planned Analyses

Any changes to the planned statistical analyses made will be documented in a Statistical Analysis Plan approved prior to database lock.

6 VALIDATION

All clinical data reports generated per this plan will be validated per [90702587](#), Global WI: Clinical Data Reporting Validation.

7 PROGRAMMING CONSIDERATIONS

7.1 Statistical Software

All statistical analyses will be performed using the SAS System software, version 9.2 or later (Copyright© 2000 SAS Institute Inc., [name], USA. All rights reserved).

All statistical analyses will be conducted according to applicable Standard Operating Procedures, Work Instructions, and the study-specific statistical analysis plan.

7.2 Format of Output

Results of analysis will be output programmatically to Microsoft Office® Word documents from SAS with no manual intervention. All output for the final statistical report will be in the form of a Word document containing tables, figures, graphs, and listings, as appropriate, or in Excel format.

7.3 Methods for Handling Missing Data

All subjects who are enrolled will be eligible for evaluation. Handling of dropouts and missing data will depend on their frequency and the nature of the outcome measure. All data will be included in the analysis unless judged to be invalid.

When calculating rates of adverse events, missing and partial dates will be handled as shown in the table below.

Partial Date	Action Taken
Entire adverse event onset date is missing	The procedure date will be used for the onset date.
The month and the day of the month are missing but the year is available	January 1 st will be used for the month and day of the onset date. However, if the imputed date falls before the procedure date, then the procedure date will be used for the onset date.
Day is missing, but the month and year are available	The 1 st will be used as the day of the onset date. However, if the imputed date falls before the procedure date, then the procedure date will be used for the onset date.

